9.3 Restarting Ixazomib

Whether ixazomib can be restarted after a treatment interruption will depend on reason for the interruption; and if an adverse event (AE) its severity and its duration.

9.3.1 Interruption ≤28 Days:

- Ixazomib treatment can be restarted with dose modification as specified according to the type of adverse event. Dose up-titration back to ixazomib doses used during prior cycles associated with an adverse event will not be permitted.

9.3.2 Interruption >28 Days:

- **For an AE:** Treatment cannot be restarted after an interruption of >28 days because of a persisting AE. Ixazomib will be permanently discontinued, and the patient discontinued from the study and will proceed to complete assessments and procedures for early discontinuation (See 15.0 Early Discontinuation).
- **For Other Reasons:** If treatment is interrupted for >28 days for any other reason, ixazomib treatment can be restarted at the discretion of the investigator. If treatment is restarted, the ixazomib dose will be the most recent dose level being used prior to the interruption.

After restarting therapy, study visits will continue to be scheduled relative to Day 1 of study participation. The total study duration will be 28-29 weeks, starting with Day 1, and if dosing is interrupted, the study duration will remain unchanged.

9.4 Ixazomib Supply

Ixazomib 4 mg, 3mg, and 2.3 mg capsules are being supplied by Takeda.

Ixazomib will be labeled and handled as open-label material, and packaging labels will fulfill all requirements specified by governing regulations.

The capsules are individually packaged using cold-form foil-foil blisters that are in a child-resistant carton. There are 3 capsules in each wallet/carton.

Upon receipt at the investigative site, ixazomib should remain in the blister and carton provided until use or until drug is dispensed. The container should be stored at the investigative site at room temperature (2°C to 30°C). Ensure that the drug is used before the retest expiry date provided by Takeda. Expiry extensions will be communicated accordingly with updated documentation to support the extended shelf life.

Ixazomib capsules dispensed to the patient for take-home dosing should remain in the blister packaging as noted above until the point of use. The investigative site is responsible for providing the medication to the patient in the correct daily dose configurations.

Comprehensive instructions should be provided to the patient in order to ensure compliance with dosing procedures. Patients who are receiving take-home medication should be given only 1 cycle of medication at a time. Patients should be instructed to store the medication at room temperature (2°C to 30°C) for the duration of each cycle. Patients should be instructed to return their empty blister packs to the investigative site, rather than discarding them. Reconciliation will occur accordingly when the patient returns for their next cycle of take-home medication. Any extreme in temperature should be reported as an excursion and should be dealt with on a case-by-case basis.

9.5 Dispensing of Ixazomib

Beginning on study on Day 1, and at each subsequent study visit, a 4-week supply (3 doses) of ixazomib will be dispensed to the participant for consumption during the next 28 day cycle. The day 1 dose for that cycle will be observed taken by a member of the study team during at the time of dispensing. Participants will be instructed to store day 8 and day 15 ixazomib doses at room temperature not to exceed 30°C /86°F and to return all used and unused capsules of ixazomib.

9.6 Ixazomib Accountability

The monitoring of the ixazomib inventory may be delegated to the responsible pharmacist; however, the investigator will be ultimately responsible for monitoring of the inventory. Ixazomib will not be used for any purpose other than that described in the protocol, and it will be stored in a secure place with access restricted to authorized personnel.

Participants will return all used and unused capsules of ixazomib at each study visit.

Investigational ixazomib (expired or end of study) should be destroyed on site according to the institution's standard operating procedure. Be sure to document removal and destruction on drug accountability logs.

10.0 BACKGROUND MEDICATION MMF

The study will enroll participants who either are not on background SSc-ILD medication or are on a background stable dose of MMF (see Study Population 8.1.2 SSc and SSc-ILD Related Criteria). MMF will be treated as background medication and will continue to be prescribed as part of usual clinical care. MMF will not be provided as part of the study. Participants on MMF will continue to take MMF during the study. Background MMF cannot be switched to another agent, nor is the addition of other background medications permitted; if this is necessary, the patient will be discontinued from the study and will proceed to complete early discontinuation assessments and procedures. Changes in the dose of the background MMF are not planned during the study; but if patient management requires a dose adjustment within the established limits of MMF ≤ 1.5 g BID, the patient will remain in the study. Changes within the allowable dose range of MMF will not be considered a deviation. MMF can produce significant adverse effects, including effects on the GI system, skin, liver, and central nervous system. Participants will be monitored for adverse effects of MMF when being used concurrently with ixazomib.

11.0 OTHER PRIOR THERAPIES

Any prior use of ixazomib or other proteasome inhibitor, rituximab, or oral or intravenous cyclophosphamide will exclude participation in this study (See 8.2.4 Eligibility Criteria Medication Exclusions).

Patients wishing to participate who are taking medications specifically for SSc-ILD other than MMF or any other excluded medication (see 8.2.4 Eligibility Criteria Medication Exclusions) will be required to discontinue that medication and undergo medication washout (See Study Assessments By Visit 18.1 – Washout Period). After completing medication washout, the participant can be screened for study eligibility.

Bronchodilator use will be prohibited in the 24 hours before pulmonary function testing and ECG tests throughout the study.

12.0 CONCOMITANT THERAPIES

Concomitant therapies are any therapies used from the time that informed consent is obtained the day of the last study visit. Therapies that are considered necessary for the patient's welfare may be given at the discretion of the investigator, with careful monitoring for new signs or symptoms. All the following will be considered concomitant medications and will be recorded at each study visit:

- Prescription drugs
- Over-the-counter drugs (e.g., antacids or eye drops)
- Vitamins, herbal preparations, dietary supplements, and homeopathic preparations
- Prohibited drugs (See 13.0 Prohibited Therapies)

Oral corticosteroids are used with caution in scleroderma because of their potential for triggering SSc renal crisis if corticosteroid dose equivalents of > 15 mg/day prednisone are used. However, oral corticosteroids will be permitted if clinically indicated during the study, provided the dose does not exceed the equivalent of prednisone 10 mg/day.

The following medications and procedures are permitted during the study:

- Antiemetics, including 5-HT3 serotonin receptor antagonists, may be used at the discretion of the investigator.
- Loperamide or other antidiarrheal should be used for symptomatic diarrhea at discretion of the investigator. The dose and regimen will be according to institutional guidelines. Intravenous fluids should be given to prevent volume depletion.
- Growth factors (e.g., granulocyte colony stimulating factor [G-CSF], granulocyte macrophage-colony stimulating factor [GM-CSF], recombinant erythropoietin) are permitted. Their use should follow published guidelines and/or institutional practice. Erythropoietin will be allowed in this study. Their use should follow published guidelines and/or institutional practice.
- Patients should be transfused with red cells and platelets as clinically indicated and according to institutional guidelines.
- Antiviral therapy such as acyclovir may be administered if medically appropriate.
- Patients who experience worsening neuropathy from baseline may be observed for recovery and have dose reductions/delays as indicated in the protocol, and any supportive therapy or intervention may be initiated as appropriate at the discretion of the investigator.
- Supportive measures consistent with optimal patient care may be given throughout the study.

Participants will be monitored for any adverse effects related to concomitant therapies used concurrently with ixazomib.

13.0 PROHIBITED THERAPIES

Medications listed in 8.2.4 Eligibility Criteria Medication Exclusions are additionally prohibited during participation in this study. If a participant receives any of these prohibited therapies, the therapies will be recorded, and the participant will be discontinued from the study. The participant will proceed to complete early discontinuation assessments and procedures (see 15.0 Early Discontinuation).

Systemic treatment with any of the following metabolizing enzyme inducers should be avoided, unless there is no appropriate alternative medication for the patient's use (Rationale: If there were to be a drug-drug interaction with an inducer, ixazomib exposure would be decreased):

- Strong CYP3A inducers: rifampin, rifapentine, rifabutin, carbamazepine, phenytoin, and phenobarbital.

- If use of one of these CYP3A inducing medications is required, the participant will be discontinued from the study. The participant will proceed to complete early discontinuation assessments and procedures.

The following medicinal products and procedures are prohibited during the study:

- Excluded foods and dietary supplements include St. John's wort.
- Platelet transfusions to help patients meet eligibility criteria are not allowed within 3 days prior to study drug dosing for any dosing day.

14.0 PREGNANCY

It is not known what effects ixazomib has on human pregnancy or development of the embryo or fetus. Therefore, female patients participating in this study should avoid becoming pregnant, and male patients should avoid impregnating a female partner. Nonsterilized female patients of reproductive age group and male patients should use effective methods of contraception through defined periods during and after study treatment as specified below.

14.1 Female patients

Female patients must meet 1 of the following:

- Postmenopausal for at least 1 year before the screening visit, or
- Surgically sterile, or
- If they are of childbearing potential, agree to practice 2 effective methods of contraception from the time of signing of the informed consent form through 90 days after the last dose of study drug (See 8.1.3 Study Population Informed Consent and Protocol Adherence), or
- Agree to practice true abstinence, when this is in line with the preferred and usual lifestyle of the subject. (Periodic abstinence [e.g., calendar, ovulation, symptothermal, postovulation methods] and withdrawal are not acceptable methods of contraception.)

14.2 Male patients

Male patients even if surgically sterilized (i.e., status post-vasectomy) must agree to 1 of the following:

- Practice effective barrier contraception during the entire study treatment period and through 90 days after the last dose of study drug (See 8.1.3 Study Population Informed Consent and Protocol Adherence), or
- Agree to practice true abstinence, when this is in line with the preferred and usual lifestyle of the subject. (Periodic abstinence [e.g., calendar, ovulation, symptothermal, postovulation methods for the female partner] and withdrawal are not acceptable methods of contraception.)

15.0 EARLY DISCONTINUATION

Patients will be free to discontinue their participation in the study at any time and without prejudice to further treatment. In addition, patients will permanently discontinue study

drug and will be discontinued from study for any of the following reasons:

- Unacceptable toxicity
- Interruption of study treatment for >28 days because of an AE(s)
- Patients who were on no background SSc-ILD medication at study entry and need to begin a SSc-ILD medication:
 - A decline of FVC by $\geq 15\%$ predicted or a decline of DLCO by $\geq 15\%$ predicted observed during the study that is sustained 4 weeks, or a decline of FVC itself to $<45\%$ predicted or decline of DLCO itself to $<40\%$ predicted observed during the study and if not explained by alternative etiology other than worsening scleroderma-related ILD as confirmed by HRCT chest scan will be considered meaningful differences in regards to the participant's background pulmonary status. In such an event, the patient will be discontinued from the study and will proceed to complete early discontinuation assessments and procedures.
- Patients on background MMF at study entry who need either (1) to switch to another background SSc-ILD medication, or (2) to begin additional treatment with another background SSc-ILD medication:
 - A decline of FVC by $\geq 15\%$ predicted or a decline of DLCO by $\geq 15\%$ predicted observed during the study that is sustained 4 weeks, or a decline of FVC itself to $<45\%$ predicted or decline of DLCO itself to $<40\%$ predicted observed during the study and if not explained by alternative etiology other than worsening scleroderma-related ILD as confirmed by HRCT chest scan will be considered meaningful differences in regards to the participant's background pulmonary status. In such an event, background MMF may not be switched to another agent in the study nor is the addition of other background medication permitted in the study; if this is necessary, the patient will be discontinued from the study and will proceed to complete early discontinuation assessments and procedures.
- Need for a prohibited medication
- Pregnancy
- Organ, stem cell, or bone marrow transplant
- At the discretion of the investigator

For participants taking no background SSc-ILD medication at study entry who need to begin a SSc-ILD medication and participants on background MMF at study entry who need either (1) to switch to another background SSc-ILD medication, or (2) to begin additional treatment with another background SSc-ILD medication, the new SSc-ILD medication will be prescribed as routine clinical care and will not be provided as part of the study.

Participants who prematurely and permanently discontinue ixazomib study treatment will return to the clinic as soon as possible after the last dose of ixazomib and not later than 10 days after that dose to complete early discontinuation assessments and procedures as planned for study day 168 (week 24) office visit (see 18.3.10).

Participants who prematurely and permanently discontinue ixazomib study treatment will

again return to the clinic 28-35 days after completing the study early discontinuation assessments and procedures visit to complete early discontinuation assessments and procedures as planned for study post-treatment follow-up day 196-203 (week 28-29) office visit (see 18.3.11).

Any patient who prematurely and permanently discontinues ixazomib study treatment will be discontinued from the study and will be encouraged to continue post-discontinuation monitoring if eligible to do so.

15.1 POST-DISCONTINUATION MONITORING FOR SAFETY AND EFFICACY OBJECTIVES

15.1.1 Eligibility for Post-Discontinuation Monitoring for Safety and Efficacy Objectives

Participants who have prematurely and permanently discontinued ixazomib study medication for any of the following reasons will be encouraged to continue monitoring for safety and efficacy objectives:

- Unacceptable toxicity
- Interruption of study treatment for >28 days because of an AE(s)
- Patients who were on no background SSc-ILD medication at study entry and need to begin a SSc-ILD medication
- Patients on background MMF at study entry who need either (1) to switch to another background SSc-ILD medication, or (2) to begin additional treatment with another background SSc-ILD medication
- Need for a prohibited medication
- At the discretion of the investigator

15.1.2 Post-Discontinuation Monitoring Visits

Based on the date of completion of the early discontinuation assessments and procedures as planned for study day 168 (week 24), eligible participants will continue to be monitored and evaluated subsequently every 28 days (\pm 4 days) for safety and efficacy objectives.

Participants initiating post-discontinuation monitoring visits will not complete the study early follow-up office visit (day 196-203) assessments and procedures (see 15.0).

15.1.3 Post-Discontinuation (PD) Monitoring Visit 1 (PD day 28 \pm 4 days), Visit 2 (PD day 56 \pm 4 days), Visit 4 (PD day 112 \pm 4 days), and Visit 5 (PD day 140 \pm 4 days) as necessary

Post-discontinuation monitoring visits PD Visit 1, PD Visit 2, PD Visit 4, and PD Visit 5 as necessary will include the following assessments and procedures:

1. Directed medical history including review of AEs/SAEs and concomitant medications that have been taken since the preceding visit.
2. If participant is taking background MMF, confirm dose and timing of dosing.
3. UCLA SCTC GIT 2.0 questionnaire
4. Hematology and serum chemistries blood samples
5. Clinical Immunology Tests blood sample
6. Blood sample for biomarker analyses
7. Spirometry and DLCO

15.1.4 Post-Discontinuation Visit 3 (PD day 84 ± 4 days) and Post-Discontinuation Visit 6 (PD day 168 ± 4 days) as necessary

Post-discontinuation visits PD Visit 3 and PD Visit 6 as necessary will include following assessments and procedures:

1. Directed medical history including review of AEs/SAEs and concomitant medications that have been taken since the preceding visit.
2. Physical examination, including vital signs (blood pressure, heart rate, and respiratory rate) and body weight (in kilograms)
3. If participant is taking background MMF, confirm dose and timing of dosing.
4. mRSS
5. UCLA SCTC GIT 2.0 questionnaire
6. Disease-status scales:
 - a. Mahler TDI
 - b. SHAQ
 - c. PtGA

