15.1.5 Final Post-Discontinuation Visit

Regardless of the number of post-discontinuation visits needed every 28 day ± 4 days following the date of completion of the early discontinuation assessments and procedures as planned for study day 168 (week 24), the final post-discontinuation visit will occur at a time point between what would have been study day visit 168 and study day 196-203 follow-up office visit should the participant have not prematurely discontinued ixazomib study medication. The final post-discontinuation visit will include following assessments and procedures:

1. Directed medical history including review of AEs/SAEs and concomitant medications that have been taken since the preceding visit.
2. Physical examination, including vital signs (blood pressure, heart rate, and respiratory rate) and body weight (in kilograms)
3. If participant is taking background MMF, confirm dose and timing of dosing.
4. mRSS
5. UCLA SCTC GIT 2.0 questionnaire
6. Disease-status scales:
 - a. Mahler TDI
 - b. SHAQ
 - c. PtGA

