24.6.2 Additional Assessments for Clinical Efficacy

Analysis of these additional efficacy assessments will be based on the safety population. Clinical efficacy assessments will include each of the individual components of ACR CRISS as follows:

- mRSS (modified Rodnan skin score)
- FVC % predicted
- HAQ-DI (Health Assessment Questionnaire-Disability Index)
- PtGA (Patient Global
- MDGA (Physician Global Assessment)

Additional clinical efficacy measures include:

- DLCO % predicted
- HRCT chest scan ILD severity using the Goh scoring method
- Patient reported outcome Mahler Baseline/Transitional Dyspnea Index (Mahler BDI/TDI).

The results of mRSS score and changes from baseline at study day 84 (week 12) and study day 168 (week 24) will be summarized without imputation for missing values.

The percent predicted FVC and DLCO results and change from screening at study day 28 (week 4), day 56 (week 8), day 84 (week 12), day 112 (week 16), day 140 (week 20) and study day 168 (week 24) will be summarized descriptively without imputation for missing values. Total lung capacity results and change from screening at study day 84 (week 12) and study day 168 (week 24) will be summarized descriptively without imputation for missing values.

HRCT chest scan Goh scoring of ILD severity and change from baseline at study day 168 (week 24) will be summarized descriptively.

The results for each of the disease-status scales Mahler BDI/TDI, SHAQ, PtGA and MDGA and changes from baseline at study day 84 (week 12) and study day 168 (week 24) will be summarized descriptively without imputation for missing values.

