24.8 Post-Discontinuation Clinical Efficacy Analysis

Participants who prematurely and permanently discontinue ixazomib study medication and continue monitoring with post-discontinuation visits will be used for the analysis of post-discontinuation clinical efficacy data.

24.8.1 Post-Discontinuation ACR CRISS (American College of Rheumatology Composite Response Index for clinical trials in early diffuse cutaneous systemic Sclerosis)

ACR CRISS incorporates multisystem involvement in diffuse cutaneous systemic

sclerosis/scleroderma and includes the patient's perspective and the impact of the disease on functional disability (17.3.6 Description of Study Measures, ACR CRISS).

The ACR CRISS is calculated as a 2-step process. The four individual possible outcomes of Step 1 ACR CRISS which include new scleroderma renal crisis, decline in FVC % predicted \geq 15% (relative), new decline of left ventricular ejection fraction to 45% or less attributable to scleroderma, and new onset pulmonary arterial hypertension attributable to scleroderma will be tabulated and summarized descriptively for post-discontinuation visit 3 (PD day 84 \pm 4 days) as required and the final post-discontinuation visit.

Step 2 ACR CRISS calculates changes from baseline in the predicted probability of improvement and will be applied and summarized descriptively for post-discontinuation visit 3 (PD day 84 \pm 4 days) as required and the final post-discontinuation visit.

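### Counting post-discontinuation visits from the stopping visit leaves most participants who stop before week 12 without week-12 skin, patient-reported, global or ACR CRISS values

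*Combined protocol and SAP*

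**What the plan says.** **Stopping visit.** Under Section 15.0, participants who stop permanently "return to the clinic as soon as possible after the last dose of ixazomib and not later than 10 days after that dose", and there "complete early discontinuation assessments and procedures as planned for study day 168 (week 24) office visit". That is the full set: mRSS, Mahler TDI, SHAQ (which gives HAQ-DI), PtGA, MDGA, complete lung function and HRCT.

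**Later visits.** Section 15.1.2 sets the clock at the stopping visit ("Based on the date of completion of the early discontinuation assessments and procedures as planned for study day 168 (week 24"). Visits then follow at 28-day intervals, each with a ±4-day window. PD visits 1, 2, 4 and 5 carry spirometry and DLCO as their only efficacy measures (15.1.3). PD visits 3 and 6, at PD days 84 and 168, carry the full set without HRCT (15.1.4). The final PD visit, with the full set and HRCT, is the only one tied to the Day-1 calendar: it falls "between what would have been study day visit 168 and study day 196-203 follow-up office visit" (15.1.5).

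**Restarted treatment.** For participants who restart after an interruption, Section 9.3 says "study visits will continue to be scheduled relative to Day 1 of study participation".

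**Analysis.** Section 24.6.2 plans "The results of mRSS score and changes from baseline at study day 84 (week 12) and study day 168 (week 24"), without imputation. Section 24.6.1 uses the same two days for ACR CRISS step 2. PD data are reported separately. CRISS change from baseline is "summarized descriptively for post-discontinuation visit 3 (PD day 84" ±4 days) and for the final visit (24.8.1). The individual measures are summarized as change from the stopping visit (24.8.2). No rule assigns a PD visit to a study week.

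**The concern.** Section 15.1.1 gives efficacy as one purpose of PD monitoring, and the efficacy time points are weeks 12 and 24. The monitoring calendar reaches week 24 or a little later through the final visit, but passes week 12 by for most early stoppers. These participants are still seen every 28 days, so skin and questionnaire data are lost through scheduling and not through refusal.

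The reasons for stopping include unacceptable toxicity and worsening lung disease. The week-12 tables would then mainly describe people still on drug. With 12 participants, 6 per background group, and no hypothesis test, the descriptive tables are the efficacy result, and one absent participant is 1/6 = 17% of a group. A skin score or questionnaire not taken near day 84 cannot be rebuilt in analysis.

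A second consequence is that PD visit 3 falls at a different time since baseline for each participant, while CRISS change from baseline is summarized there as a single visit.

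**Working it through.** The plan states no figure to reproduce, so the check is a count over the calendar.

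**Inputs.**
- S = study day of the stopping visit.
- PD visits at S + 28k, k = 1 to 6, each ±4 days (15.1.2 to 15.1.4).
- Full set at k = 0, 3 and 6, and at a final visit on study days 168 to 203 (15.0, 15.1.4, 15.1.5).
- FVC/DLCO at every visit.
- Week-12 window: day 84 ±4, that is days 80 to 88 (18.3.7).

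**Full set in days 80 to 88.**
- k = 0: needs S ≥ 80.
- k = 3: earliest allowed day is S + 84 − 4 = S + 80, so it needs S + 80 ≤ 88, that is S ≤ 8.
- k = 6 and the final visit: far too late.

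So S = 9 to 79 gives no full set even if the ±4 days are used on purpose: 79 − 9 + 1 = 71 days. With visits exactly on time, k = 3 needs S ≤ 4, and the gap is S = 5 to 79, or 75 days.

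**Share of stoppers before day 84.** The documents give no distribution of stopping days, so two are assumed.

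| Assumed stopping visit | No full set, windows used | No full set, visits on time |
|---|---|---|
| Uniform on days 1 to 83 | 71/83 = 86% | 75/83 = 90% |
| Last dose on a dosing day of cycles 1 to 3, visit 0 to 10 days later | 88/99 = 89% | 93/99 = 94% |

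Under the uniform assumption the nearest full set is a median of 21 and at most 42 days from day 84.

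**FVC/DLCO for S = 9 to 79.** On time, a visit lands in the window for S = 24 to 32 and 52 to 60: 18/71 = 25%. With windows used, for S = 20 to 36 and 48 to 64: 34/71 = 48%. Visits are 28 days apart, so one is never more than 14 days from day 84. A stop on day 28 or 56 gives FVC/DLCO exactly on day 84; a stop on day 42 gives days 70 and 98.

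**Where PD visit 3 falls.** Study day S + 84: 9 + 84 = 93 (93/7 = 13.3 weeks) to 79 + 84 = 163 (163/7 = 23.3 weeks). Week 29 (day 203) needs S = 203 − 84 = 119, and that participant was still on the study calendar at day 84.

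**Extension.** The same arithmetic applies to week 36 (extension day 84 ±4). Extension PD visits 1, 2, 4 and 5 include no lung function (25.4.2.1), so for stopping visits on extension days 9 to 79 FVC/DLCO are absent from the window too. Section 25.5.4.2 takes mRSS change from baseline and lung-function change from screening at PD day 84, so there the mixed time since baseline affects these measures as well as CRISS.

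**The case against.** The clock anchored at stopping has a purpose. For the change-from-stopping summaries in Section 24.8.2, PD day 84 is a common time point, about 84 days after the stopping assessment. That stands, and those summaries can stay. The mixed time since baseline matters, in the initial study, mainly for CRISS in 24.8.1.

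The loss is also limited. Every stopper is due a full set within 10 days of the last dose, and the final visit gives another at or after week 24, so one intermediate time point is lost. A fixed visit about 28 days after the stopping visit is useful in a trial whose primary objective is safety, and a change should not remove it. Both points stand.

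A reader might infer more than the documents support:
- *That early stoppers have no week-12 efficacy data at all.* FVC and DLCO are efficacy measures, are taken at every PD visit, and always lie within 14 days of day 84.
- *That nothing after stopping follows the Day-1 calendar.* The final visit does, although it may fall anywhere from day 168 to day 203.
- *That Section 9.3 contradicts Section 15.1.2.* Section 9.3 covers participants who restart drug, not those who stop for good.
- *That an error rate or the primary result is affected.* Section 24.2 plans no hypothesis test, and these measures are secondary.

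**Conclusion.** The concern holds for the week-12 values of mRSS, HAQ-DI, PtGA, MDGA, TDI, TLC and ACR CRISS. For a stopping visit on any of study days 9 to 79, none can fall in day 84 ±4. This follows from the calendar and needs no assumption about when people stop. The shares of 86 to 94% do rest on the assumed stopping days; most stoppers would keep a week-12 set only if stops clustered on about days 1 to 8 or 80 to 83. For FVC/DLCO the finding is weaker: between a quarter and a half of these stopping days still give a value in the window.

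CRISS at PD visit 3 mixes values from about study weeks 13 to 23 for these participants, and up to week 29 when later stoppers are added.

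The point applies only to stoppers who are eligible for monitoring and agree to it; those who decline remain missing under any schedule. The documents give no expected number of stoppers, so the total effect cannot be sized beyond 1 in 6 of a group for each. The change is worth making because it recovers a planned time point at small cost.

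**What to change.** **Schedule (15.1.2 to 15.1.5).** After the stopping visit, hold the remaining monitoring visits on the Day-1 calendar: days 28, 56, 84, 112, 140 and 168, each ±4. Use the 15.1.4 list at study day 84 and the 15.1.5 final list at day 168. Never skip day 84 or day 168. Any other visit may be skipped if it falls within 14 days of the stopping visit. (Applied to every visit, that skip rule would drop day 84 for stops on days 70 to 79, and day 168 for late stoppers.)

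**Safety.** Keep a check with laboratory tests about 28 days after the stopping visit when no calendar visit falls near it, and state what counts as near.

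**Analysis (24.8).** Report CRISS and its components by study week, in addition to change from the stopping visit, so that the values can be shown beside weeks 12 and 24.

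**Extension.** Make the matching change in 25.4.2, so that lung function and the rest of the full set are obtained at extension day 84, and in the summaries of 25.5.4.

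**Cost.** Counting the current plan as 28-day steps from the stopping visit until one reaches day 168, the new calendar needs the same number of monitoring visits for 106 of the 162 stopping days 2 to 163, and one fewer for the other 56. For example, a stop on day 50 gives days 78, 106, 134, 162 and 190 now (5 visits), against 84, 112, 140 and 168 (4 visits).

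The added laboratory check is not in that count. For stopping days 9 to 79 it is needed on 21 of 71 days (30%) if near means within 10 days, and on 53 of 71 (75%) if it means within 4. The first monitoring visit also becomes less regular: 5 to 42 days after the stopping visit for these stops, instead of 28 ±4.
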